3.3 Exclusion criteria

Patients who meet any of the following exclusion criteria will be excluded. Laboratory tests related to the exclusion criteria will be assessed based on central laboratory measurements. If a given laboratory test is performed multiple times during the screening period, the most recent test will be used for assessment. If blood is drawn on the day of dialysis, data before dialysis will be used for assessment.

- (1) Patients with anaemia resulting primarily from a disease other than CKD after date of consent (e.g., sickle-cell syndrome, myelodysplastic syndrome, myelofibrosis, haematopoietic malignancy, myeloma, haemolytic anaemia, thalassemia, or aplasia pure red cell)
- (2) Patients with active haemorrhaging or exsanguination within 8 weeks prior to the first day of the screening period
- (3) Patients who have received RBC transfusion within 8 weeks prior to the first day of the screening period
- (4) Patients who have received testosterone enanthate or mepitiostane within 8 weeks prior to the first day of the screening period
- (5) Patients determined by investigators/subinvestigators to likely require immediate rescue therapy or drug holiday of the study drug after initiation of treatment period

- (6) Patients who are expected to no longer require hemodialysis or hemodiafiltration due to recovery of renal function
- (7) Patients with AST, ALT, or total bilirubin values of 2.5 times or greater the upper limit of standard during the screening period. This does not apply to patients with Gilbert's syndrome.
- (8) Patients with poorly controlled hypertension (defined as a systolic blood pressure (BP) of >180 mmHg or diastolic BP of >110 mmHg) on the first day of the screening period and on the first day of the treatment period
- (9) Patients for whom any of the following apply upon funduscopy during the screening period:
 - ✓ No ocular fundus findings are possible.
 - ✓ Active ocular fundus disease
- (10) Patients with severe cardiac failure from the day of consent (Class IV according according to severity classification of the New York Heart Association [NYHA])
- (11) Patients with cerebrovascular disorders or acute coronary syndromes (hospitalization for unstable angina or myocardial infarction, etc.) within 12 weeks prior to the first day of the screening period. Patients who have been hospitalized due to acute coronary angioplasty or cardiac failure.

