3.4 Re-testing/re-screening

(1) Re-testing

Re-testing may be performed during the screening period at the discretion of the investigator/subinvestigator for any subject whose laboratory values (Hb, serum ferritin, TSAT, folic acid, vitamin B₁₂, AST, ALT, and total bilirubin) or BP do not meet the inclusion criteria or meet the exclusion criteria during the screening period.

Subjects with blood pressure measurements on the first day of the treatment period which meet exclusion criteria may be re-tested at the discretion of investigators/subinvestigators, and processed for treatment period initiation if they no longer meet exclusion criteria.

However, the maximum time from the first day of the screening period to the first day of the treatment period is 6 weeks.

(2) Re-screening

For any subject whose laboratory values (Hb, serum ferritin, TSAT, folic acid, vitamin B₁₂, AST, ALT, and total bilirubin), BP, or BP measurements on the first day of the treatment period do not meet the inclusion criteria or meet the exclusion criteria during the screening period, re-screening may be performed if the investigator/subinvestigator considers that the subject may become eligible for the study due to natural course or with drug therapy.

However, re-screening may only be performed once for any given subject.

4. Explanations to subjects and consent

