5.2 Study design

This is a multicenter, uncontrolled, open-label study.

(1) Screening period

The screening period begins on the first day of the screening period, and ends upon completion of tests required on the first day of the treatment period. Maximum screening period time is 6 weeks. Two visits will be made during the screening period; the first (SV1) is the first day of the screening period. The second screening period visit (SV2) occurs after results from laboratory tests performed on the first day of the screening period have been obtained. Testing may be repeated as necessary.

(2) Treatment period

The treatment period will last from completion of scheduled tests on the first day of the treatment period to completion of blood sampling for haematology tests on the final day of the treatment period (Week 24 of the treatment period or discontinuation of treatment).

During the treatment period, subjects are to visit the study site on the day of dialysis after a 2-day interdialytic interval; however, if this is difficult, subjects are to visit the study site on the day of dialysis after a 1-day interdialytic interval. After the first day of the treatment period, subjects are to visit the study site every 2 weeks until Week 12 and every 4 weeks after Week 12 to undergo the scheduled test. However, subjects are to visit the study site at shorter intervals as necessary, if excessive increases or decreases in Hb are of concern based on the time course of Hb levels or for hemodialysis.

(3) Follow-up observation period

The follow-up observation period consists of 2 weeks from completion of blood sampling for haematology tests on the final day of the treatment period. The final day of the follow-up observation period is 2 weeks from the completion of blood sampling for haematology tests on the final day of the treatment period, regardless of whether a study visit is made on that day.

Subjects should make study visits as close to the same time as possible during the study period for scheduled tests.

Rationale

Screening period: Established to confirm subject suitability for the study.

Treatment period: An uncontrolled study design was selected in consideration of feasibility due to the extremely small number of HD-CKD patients in Japan who are not treated with any ESA formulation.

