8.6.3 Lifestyle guidance

Investigators/subinvestigators or clinical coordinators will give guidance to subjects covering the following points.

- (1) Subjects receive examinations and tests on scheduled days. Subjects should always contact the study center if unable to make a scheduled study visit, and follow instructions.
- (2) Subjects should contact investigators/subinvestigators in a timely manner if they experience abnormal symptoms.
- (3) Subjects will receive a study participation card to show when receiving care at other departments or hospitals. Subjects should always inform investigators/subinvestigators or clinical coordinators if they are using any drugs prescribed by other doctors or purchased at a pharmacy. Subjects should always consult with investigators/subinvestigators or clinical coordinators before using any new drugs during the study.
- (4) Maintain the same lifestyle (daily activities, food, etc.) as before to the extent possible.
- (5) Investigators/subinvestigators or clinical coordinators will instruct women who may become pregnant to use the contraception methods described below during the study period and up to 30 days following the final dose of the study drug, and men during the study period and up to

90 days following the final dose of the study drug. Calendar, anovulation, ovulation detection through body temperature, post-ovulation, and withdrawal do not constitute appropriate forms of contraception. This does not apply to postmenopausal women with absence of menstruation for more than 1 year, women with surgical hysterectomy, or women with bilateral ovariectomy.

- 1) Abstain from intercourse
- 2) Use two effective types of contraception. Joint use of a barrier method (latex condoms for men or diaphragm) in conjunction with a highly effective method such as oral contraceptives, IUD, tubal ligation, or vasectomy is recommended.

- [a] Maximum screening period length is 6 weeks. Test results will be reviewed prior to transitioning from the first day of the screening period to screening period Visit 2, and from screening period Visit 2 to the first day of the treatment period. Re-testing will be performed as necessary.
- [b] During the treatment period, subjects are to visit the study site on the day of dialysis after a 2-day interdialytic interval; however, if this is difficult, subjects are to visit the study site on the day of dialysis after a 1-day interdialytic interval.

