Fundoscopy will be performed once each within the screening period, from treatment period Week 20 to Week 24, and to extent possible within 14 days of study withdrawal. An ophthalmologist will perform the fundoscopy and make evaluations according to the 3-point scale below. Ophthalmologist evaluations will be recorded in CRFs. Fundoscopy images and ophthalmologist evaluations will be stored at study centers.

- 1) Normal
- 2) Clinically non-problematic abnormality
- 3) Clinically problematic abnormality (retinal hemorrhage yes/no, retinal oedema yes/no)

(8) Chest X-ray

Fundoscopy will be performed once each within the screening period, from treatment period Week 20 to Week 24, and to extent possible within 14 days of study withdrawal. Investigators/subinvestigators will evaluate test results according to the 3point scale below. Evaluation results will be recorded in CRFs. Chest X-rays will be stored at the study center.

- 1) Normal
- 2) Clinically non-problematic abnormality
- 3) Clinically problematic abnormality

(9) Pregnancy tests (only for women who may become pregnant)

Blood sampling and pregnancy testing will be performed on the first day of the screening period, treatment period Week 24, and the day of discontinuation of treatment. Investigators/subinvestigators will evaluate pregnancy based on test results and interview when appropriate. Evaluation results will be recorded in CRFs. If the subject is incapable of becoming pregnant, the reason for this will be recorded in CRFs (women only).

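### The only pregnancy test scheduled before first dose is on the first screening day, so its result can be up to 42 days old when dosing starts

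*Protocol*

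**What the plan says.** Protocol 9.2.4.1 (9) sets the schedule for women who may become pregnant: "pregnancy testing will be performed on the first day of the screening period, treatment period Week 24, and the day of discontinuation of treatment". It adds that the investigator "will evaluate pregnancy based on test results and interview when appropriate". Visit 2 and the first treatment day are not in the list.

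Section 3.4 states that "the maximum time from the first day of the screening period to the first day of the treatment period is 6 weeks", and 5.2 gives the same maximum for screening. Under 8.2.3 the investigator reviews all tests done up to the first treatment day and then decides suitability. Table 9.1-1 note *2 defines the first treatment day as the day of that decision, and 8.3 (3) has the first dose taken that day, once the required tests are done.

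Exclusion (21) in 3.3 bars pregnant, possibly pregnant and nursing women. The stated reason is that reproductive and developmental safety in humans is not established.

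Unscheduled testing is open: 5.2 says "Testing may be repeated as necessary" and footnote [a] to the schedule says "Re-testing will be performed as necessary". For exclusion criteria generally, 3.3 provides that "Laboratory tests related to the exclusion criteria will be assessed based on central laboratory measurements" and that "If a given laboratory test is performed multiple times during the screening period, the most recent test will be used for assessment".

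**The concern.** Exclusion (21) has to be true when exposure starts, not only when screening starts. A recent negative test is the direct check of that, yet the plan requires none between the first screening day and the first dose. The suitability decision can therefore rest on a result several weeks old.

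The plan treats some other safety items differently. Exclusion (8) has blood pressure checked "on the first day of the screening period and on the first day of the treatment period", and 9.2.4.1 (1) repeats haematology, biochemistry and C-reactive protein on the first treatment day.

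What is at stake is avoidable embryonic or fetal exposure in a small number of women. The trial's estimates are not at stake.

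**Working it through.** **Inputs**
- Scheduled pregnancy tests: first screening day, Week 24, day of discontinuation (9.2.4.1 (9)).
- Longest interval from first screening day to first treatment day: 6 weeks (3.4, 5.2).
- Suitability decision and first dose: both on the first treatment day, Day 0 (8.2.3, 8.3 (3), Table 9.1-1 and its note *2).
- Week 24 reference date: Day 168 (Table 9.1-1).
- Limit L on the age of the result at first dose: not in the documents. I take 7 and 14 days as examples.
- Typical screening length S: not in the documents. I take 7, 14 and 28 days, with 42 as the ceiling.

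**Maximum age of the scheduled result at first dose**

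6 weeks × 7 = 42 days.

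**Reduction from a limit L: max(S − L, 0)**

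- S = 42, L = 7: 42 − 7 = 35 days
- S = 42, L = 14: 42 − 14 = 28 days
- S = 28, L = 7: 28 − 7 = 21 days
- S = 14, L = 7: 14 − 7 = 7 days
- S of 7 or less, L = 7: 0 days, because the existing test already meets the limit

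**Gap between scheduled tests for a woman who stays on treatment**

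By reference dates, up to 42 + 168 = 210 days. With a test within 7 days of first dose this becomes at most 7 + 168 = 175 days. The 168 days on treatment are unchanged.

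**Does any other provision require a test near first dose?**
- Contraception (exclusion (20), 8.6.3 (5)) covers the interval but is not a test.
- Interview is left to the investigator's view of when it is appropriate.
- Re-testing under 3.4 is discretionary, follows a failed value, and lists Hb, ferritin, TSAT, folic acid, vitamin B12, AST, ALT, bilirubin and blood pressure. Pregnancy is not listed.
- The general re-testing wording in 5.2 and footnote [a] obliges no particular test.
- The most-recent-result rule in 3.3 matters only if a second test has been done.
- Withdrawal on discovery (12.1 (7)) and pregnancy reporting (11.3) apply once a pregnancy is known, possibly after exposure.

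None does.

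**Schedule grids.** The protocol's grid is not legible in the copy reviewed. The SAP 2.2 grid has shifted columns (its folic acid row, for example, does not match the protocol text), so it is evidence neither way. The check rests on the text of 9.2.4.1 (9).

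**The case against.** The strongest reply is that no standard in the documents is breached. The plan sets no limit on the age of a pregnancy result, so every figure beyond 42 days subtracts a limit chosen by the reviewer. The age of a result is also not a risk: the number of women of childbearing potential is unknown, and 42 days needs screening of maximum length. That stands, and it is why the point is graded minor.

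The controls in place are also substantial. Women are to abstain or use two effective methods, with calendar, temperature and withdrawal methods ruled out (8.6.3 (5)), and refusal is itself an exclusion. The study period begins at consent, so contraception starts no later than the screening test, and before it for women who wash out an ESA for 1 to 4 weeks. Exclusion (21) also lets an investigator exclude on suspicion alone. This lowers the chance of a missed pregnancy but does not remove it. Contraception depends on adherence and cannot prevent a conception before consent, and as general clinical reasoning an early test can miss a very recent one.

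Two further points have some weight. Other eligibility checks, such as fundoscopy and folic acid with vitamin B12, are also scheduled once in screening, so the contrast with blood pressure is illustrative only. And the lists in 9.2.4.1 contain slips: item (6) omits the first screening day for blood pressure although exclusion (8) needs it, and item (8), on chest X-ray, opens by naming fundoscopy. The pregnancy list could be incomplete too, which keeps confidence at medium. As written, though, it is clear and nothing contradicts it.

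**Conclusion.** The concern holds, as a minor and optional tightening. On the protocol text, the only scheduled pregnancy result available at the suitability decision can be up to 42 days old, and no other provision requires a later test before first dose. The plan is not inconsistent on this point.

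The 42-day figure is a ceiling that assumes the full 6 weeks of screening. It also assumes that re-screening starts a new first screening day with a new pregnancy test. The protocol does not say so for this test; if it were not repeated, the result could be older. The benefit cannot be sized further, because neither the typical screening length nor the number of women of childbearing potential among the 20 subjects is stated. It may be nil for many subjects.

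**What to change.** In 9.2.4.1 (9) and the schedule, require for women of childbearing potential a negative pregnancy result from a sample taken within 7 days before first dose, available before the 8.2.3 decision. Seven days is an example; the sponsor should state its own limit.

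- Preferred route: add the assay to the Visit 2 blood sent to the central laboratory.
- No extra test if the first-screening-day sample already falls within the limit.
- If Visit 2 is too early (Table 9.1-1 gives it no fixed date), allow a local test on the first treatment day before dosing, and write this into 3.3 as an explicit exception to the central-laboratory rule. The local route is needed because the decision and first dose fall on the same day and the contract laboratory's turnaround time is not stated.

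The cost is one sentence in 9.2.4.1 (9), one schedule entry and one exception in 3.3. In practice it means an extra assay or tube for a few women, since footnote [k] limits Visit 2 haematology to Hb, and a local test for those whose Visit 2 is too early. The change adds no test during the roughly 24 weeks of dosing.

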9.2.4.2 Adverse events

AEs are all clinically problematic or unplanned signs (including clinically significant abnormal laboratory values), symptoms, or illnesses occurring after administration of the study drug during the safety evaluation period, regardless of causal relationship with the study drug. Instances of aggravation of events (in terms of severity or seriousness) are treated as new AEs.

However, AEs occurring from informed consent to the first day of the treatment period which match criteria for serious adverse events are still reported to the study sponsor according to “11.1 Responses to occurrence of serious adverse events.”

(1) Symptoms and diseases

Investigators/subinvestigators will confirm AEs through interviews and examinations.

(2) Objective findings

Objective findings determined clinically problematic abnormalities* by investigators/subinvestigators are treated as AEs.

*Clinically problematic abnormalities are determined according to the following criteria.

- If related to clinical signs or symptoms.
However, if the sign or symptom has already been separately reported as an AE, the relevant laboratory test abnormality does not require treatment as adverse event.
- If the relevant laboratory test abnormality was treated medically or surgically.
- If the relevant laboratory test abnormality causes a change in method of administration of the study drug (dosage change, drug holiday, discontinuation, etc.).

- If investigators/subinvestigators otherwise determine the abnormality to be clinically problematic.

(3) Adverse event evaluation and standards

1) Date of onset

Date the symptom or laboratory test abnormality was observed.

2) Severity

Adverse event severity is classified as follows:

1. Mild: No effect on activities of daily life
2. Moderate: Moderate impairment of activities of daily life caused by event
3. Severe: Event prevents performing activities of daily life

3) Seriousness

AE seriousness is classified as follows:

1. Not serious: Any events other than 2 below.
2. Serious: Any events (a) to (f):
 - (a) Fatal
 - (b) Life-threatening
 - (c) Necessitating hospitalization or prolongation of hospitalization for treatment
 - (d) Events leading to permanent or clear dysfunction or disability
 - (e) Other events or reactions judged medically significant

(f) Causing congenital anomalies or defects

4) Causal relationship with the study drug

The investigator/subinvestigator will assess whether or not there is a logical possibility that the study drug caused the AE. This assessment will take into account factors not related to the study drug, including risk factors such as natural course and concurrent treatments for underlying or concomitant diseases, as well as the temporal relationship between the study drugs and the event (recurrence after resuming administration, elimination after discontinuation, etc.). AEs for which a logical possibility of a causal relationship with the study drug exists will be treated as ADRs.

1. Logical possibility
2. No logical possibility

5) Outcome

AE outcomes are classified as follows:

1. Recovery
2. Relief
3. Not recovered
4. Recovered with sequelae
5. Death
6. Unknown

6) Date of outcome

Date of outcome is determined according to the following criteria:

Recovery: Date of recovery. If date of recovery is not known, use date on which recovery was confirmed or determined.

Relief: Date on which relief was confirmed or determined.

Not recovered: Date on which "not recovered" was confirmed or determined.

Recovered with sequelae: Date on which "recovered with sequelae" was confirmed or determined.

Death: Date of death. If date is not known, use date of confirmation or determination.

Unknown: Date of death if outcome is unknown due to death of subject for cause other than the relevant AE. For other circumstances use date of confirmation or determination.

7) Action taken with the study drug

Actions taken with the study drug are classified into the following 6 categories:

[figure not shown]
1. Discontinuation of administration (study withdrawal)
2. Drug holiday
3. Dosage increase
4. Dosage reduction
5. No action
6. Not applicable (occurred after final administration of study drug)

8) Actions taken other than with the study drug

Actions taken other than with the study drug are classified into the following two categories: If actions other than with the study drug were taken, details of these will be investigated and recorded in the CRF.

1. No
2. Yes

9) Follow-up investigation

- Period [1] above is the 14 days from the day after completion of the treatment period, during which any AEs will be investigated.
- Period [2] above is the 28 days from the day after completion of the follow-up observation period; it is the period for follow-up investigations of AEs occurring during the safety evaluation period (treatment period + Period [1]).
- Course of AEs subject to follow-up investigation during Period [2] are recorded in the subject's CRF. The date of outcome written in the CRF for AEs with outcomes of relief or not recovered is the day of observation after completion of Period [2], during Period [3].
- Further investigations (Period [3]) will be performed for the course of ADRs with outcomes of relief or not recovered as of the end of Period [2].

- If there is a valid reason to halt investigations mid-way after completion of the safety evaluation period (after completion of Period [1]), record reasons for this and conclude the follow-up investigation.

(4) Recording information in CRFs

If an AE is observed, investigators/subinvestigators will record the following information in the subject's CRF: name of AE*, date of onset, severity, seriousness, causal relationship with study drug, details of any actions taken (drug names, treatment methods, etc.), outcome, and date of outcome.

*AE names are handled in the following manner:

- Fundamentally, the name of diagnosis is used.
- The symptom name is used if a clear diagnosis has not been made.
- If there are multiple symptoms which can be expressed by a one diagnosis, that diagnosis name is used.
- Medical treatments etc. are not considered AEs; rather the disease or symptom requiring surgical treatment is considered the AE.

